## 1.0. Significance

PLWH are more likely to die from tobacco use than from HIV itself. Scalable and evidence-based smoking cessation interventions in line with current health consumer trends are highly needed in order to improve quality of life and curb mortality rates among PLWH. Moreover, the incorporation of state-of-the-art technology to improve access to hard-to-reach populations and settings has been identified as a high-priority research opportunity in the Trans-NIH Plan for HIV-Related Research. mHealth apps tailored to the specific needs of PLWH hold promise for reducing tobacco dependence among PLWH and HIV-related health disparities. However, despite promising initial evidence supporting the use of smoking cessation apps, there is a shortage of rigorous early-phase research developing and testing smoking cessation apps in general, and among PLWH specifically. The central premise of this research is that LTQ can be tailored using rigorous research methodology to meet the needs of PLWH smokers. This phase of the project will capitalize on background analytics and qualitative methods to evaluate the acceptability and preliminary efficacy of LTQ-H, a smoking cessation app iteratively designed for smokers with HIV by smokers living with HIV.

## 2.0. Goals and Aims

### 2.1. Aims

The overarching goals of this phase of the research are to evaluate the feasibility, acceptability, and preliminary efficacy of a tailored smoking cessation app for PLWH, “Learn to Quit-HIV” or “LTQ-H” for short, which was iteratively developed in the first phase of research. Specifically, we propose to conduct a feasibility, acceptability, and preliminary efficacy trial comparing LTQ-H (n=30) to an app based on U.S. Clinical Practice Guidelines only (NCI QuitGuide; n=30) among HIV-positive smokers. NCI QuitGuide will match LTQ-H’s format of delivery, dose, and duration. Both apps will be integrated with NRT and ongoing HIV clinical care. Primary outcomes: feasibility (i.e., recruitment rates, retention, app engagement); acceptability (i.e., usability, user experience, perceived utility). Secondary outcomes: cigarettes smoked per day, quit attempts, biochemically verified abstinence, NRT adherence and participant safety. Successful execution of this aim will indicate the feasibility, acceptability, and preliminary efficacy of LTQ-H.

### 2.2. Outcomes

#### Primary Outcomes:

- (1) Recruitment rates and participant retention, which will be collected and monitored throughout study duration
- (2) App engagement, which will be evaluated from background analytics data consisting of frequency and duration of app use, objective background analytics measures used in our previous work. We will use Google Analytics and our Data Transfer Agreement with smokefree.gov to gather this metric
- (3) App usability measured with the Systems Usability Scale
- (4) User Experience, extracted via thematic analysis of transcripts of semi-structured interviews. As in previous early-phase research by [name], these interviews will occur at the end of treatment (Week 12)

#### Secondary Outcomes:

- (1) Cigarettes per day (CPD) will be measured daily with the tracking feature embedded within each app. LTQ contains a feature that allows users to enter how many cigarettes they smoked at the end of the day
- (2) Quit attempts defined as self-reported no smoking at all for 24 hours, and time to 7-day relapse will be assessed via a Timeline Follow Back interview at Weeks 4, 8 and 12
- (3) 7-day point prevalence abstinence will be determined by responses to a standard self-report item (i.e., not smoking even a puff of a cigarette within the last 7 days) and breath CO<5 ppm at Week 12
- (4) Adherence to NRT will be measured daily with the app tracking feature, as well as brief interviewer-administered questionnaires at Weeks 4, 8, and 12
- (5) Participant Safety will be assessed by monitoring all adverse events during the 12-week period and in close collaboration with their medical providers

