## 4.0. Study Overview

- 1. Eligibility and Consent:** PLWH who provisionally qualify based on a phone screen will be invited to attend a remote Zoom screening visit. Informed consent will be obtained, and participants' interest in quitting, HIV and smoking statuses will be evaluated. Individuals will be screened to ensure that they own an Apple or Android smartphone, are not pregnant (if female), and are medically eligible to use NRT. Our study physician will evaluate their medical eligibility. In addition, we will obtain a signed Release of Information from potential participants to closely work with their own medical providers to monitor adverse events, dispensing of NRT, and overall participant safety.
- 2. Randomization:** Participants will be allocated to conditions using 1:1 randomization.
- 3. Interventions:** Participants will be assigned to LTQ-H or NCI QuitGuide. All participants will receive a standard 8-week course of NRT (transdermal nicotine patches starting at 21mg/24h) following recommendations contained in the U.S. Clinical Practice Guidelines.
- 4. Background Analytics:** Research staff will instruct participants on how to install the study app onto their personal smartphones and will tell them how to add a study ID in the app that will be used to retrieve background analytics information (Google Analytics) from both the LTQ-H and NCI QuitGuide apps.
- 5. Follow-Up Visits:** Visits will occur at 4, 8 and 12 weeks post-randomization. During these visits we will assess smoking and smoking abstinence, new or changes in existing adverse events and user experience with the assigned app. We will biochemically verify self-reported smoking abstinence at week 12.

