## 5.0. Interventions and Measures

### 5.1. Interventions

#### Learn to Quit-HIV (LTQ-H)

Learn to Quit (LTQ) is an Android/iOS smoking cessation app developed by [name]. It was originally developed for persons with serious mental illness (SMI). However, in this study we will be using a new version of LTQ called LTQ-H. LTQ-H was iteratively designed through a user-centered design study in persons living with HIV to evaluate key usability barriers and design requirements for this population. LTQ is based on Acceptance and Commitment Therapy (ACT), a mindfulness-based intervention with promising results for smoking cessation in several clinical trials. LTQ includes 28 Modules that encourage the learning and practice of three processes of change (e.g., awareness of urges to smoke, openness to experiencing urges, and commitment to specific values for quitting), as well as adherence to U.S. Clinical Practice Guidelines (e.g., use of medications). The app also includes ecological momentary assessments (e.g., self-tracking) of mood, nicotine replacement therapy (NRT) use, cravings to smoke, acceptance of cravings, and cigarettes smoked daily.

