#### QuitGuide (QG)

QG is an app developed by the National Cancer Institute (NCI) based on US Clinical Practice Guidelines. The app encourages users to pick a quit date upon starting the app. The app also contains mood and cigarette craving tracking, and tracking of number of days that the user was smoke-free or slipped. It also contains a journaling feature and the option to opt-in to location- or time-based notifications.

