#### 6.4. Follow-Up Visits

Participants will complete monthly follow-up (FU) visits at Weeks 4, 8, and 12 weeks post-randomization. All visits will be conducted via zoom video calling.

At each visit, participants will complete surveys to assess their smoking behavior, changes in physical or mental health (which will prompt staff to assess for adverse events), and user experience with their assigned study app. See table below for a list of all the measures.

At each visit, research staff will conduct an interview with the participant to ask about their experience using their assigned app. This interview will be audio recorded for later review. Each FU visit is expected to last between 45-60 minutes, depending on the assessment burden.

Measure	Week 4	Week 8	Week 12
Biochemical Verification (CO)			x
Health Changes Questionnaire	x	x	x
Adverse Events and Con Meds (if applicable)	x	x	x
COVID-19 & Quitting Smoking Questionnaire (Follow-up)	x	x	x
Drug Use Questionnaire (1 Month)	x	x	x
Timeline Follow-Back	x	x	x
DASS-21	x	x	x
BSI	x	x	x
Systems Usability Scale (SUS)	x		x
Qualitative user experience interview	x		x
Research Participant Perception Survey (RPPS)			x

Participants who self-report smoking abstinence by the final follow-up visit (FU3) will be mailed an iCO smokerlyzer device to do a breath test in order to biochemically verify abstinence. We will mail these to participants following their FU3 session. Once they receive the device, we will set up a short Zoom call to walk them through the CO breath test process. Staff will be on the call in order to ensure that it is the participant

who is doing the test, and that they are doing the test properly. Once the participant completes the test, we will ask them to email the result of their test to our lab email. Participants will keep these devices once they are completed in the study. The stop date for these participants will be the date of this breath test instead of the date of the FU3 visit.

Background analytics will be collected throughout the 4 months of participation, and will be measuring some things such as CPD, mood ratings, NRT use, duration of app use, and number of interactions within the app.

At the final visit (Week 12), participants will be given quitting resources if they have not quit. They will also be referred to other research studies, if eligible and willing.

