#### Secondary outcome measures include:

- Change in cigarettes smoked per day (CPD) (measured daily with the tracking feature embedded within each app)

- Quit attempts (self-reported no smoking at all for 24 hours—and *time to 7-day relapse* will be assessed via a Timeline Follow Back interview at Weeks 4, 8, and 12)
- 7-day point prevalence abstinence (not smoking even a puff of a cigarette within the last 7 days) and breath CO<5 ppm at Weeks 4, 8, and 12)
- Adherence to NRT (measured via app tracking feature and Timeline Follow-Back interview at Weeks 4, 8, and 12)
- Participant safety (adverse events)

Differences between treatment groups (LTQ-H vs. NCI QuitGuide) in terms of secondary outcomes will be assessed via chi-square tests and logistic regression or t-tests and linear regression, as appropriate:

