**t-tests and linear regression:**

- Change in CPD (measured as a continuous variable)
- Quit attempts (total number of quit attempts, measured as a continuous variable)
- Adherence to NRT (overall % of NRT used as directed, measured as a continuous variable)
- Participant safety (total number of adverse events, measured as a continuous variable)

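### Change in cigarettes per day rests only on an in-app tracker that starts after randomisation and is not described for QuitGuide, while the Timeline Follow-Back already scheduled in both arms is not named for it

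*Combined protocol and SAP*

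**What the plan says.** Section 2.2, secondary outcome (1), gives one source for the outcome: "Cigarettes per day (CPD) will be measured daily with the tracking feature embedded within each app". The sentence that follows describes count entry for one app only: "LTQ contains a feature that allows users to enter how many cigarettes they smoked at the end of the day". Section 8.2 repeats the source, "Change in cigarettes smoked per day (CPD) (measured daily with the tracking feature embedded within each app", and places the outcome under t-tests and linear regression as "Change in CPD (measured as a continuous variable". Neither section names a second source, a baseline value or a follow-up window.

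In section 5.1, the tracking features of LTQ-H include "nicotine replacement therapy (NRT) use, cravings to smoke, acceptance of cravings, and cigarettes smoked daily". For QuitGuide the text reads "The app also contains mood and cigarette craving tracking, and tracking of number of days that the user was smoke-free or slipped", with a journal and notifications besides. No cigarette count is listed.

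Two other places bear on whether both apps supply counts. Section 4.0 says that a study ID will be used to "retrieve background analytics information (Google Analytics) from both the LTQ-H and NCI QuitGuide apps". Section 6.4 says that the analytics "will be measuring some things such as CPD, mood ratings, NRT use, duration of app use, and number of interactions within the app", without saying from which app.

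Section 6.3 puts the baseline measures first, then randomisation, then installation of the assigned app. The Timeline Follow-Back (TLFB) is one of those baseline measures and recurs at Weeks 4, 8 and 12 (table in 6.4). Section 5.2 says that it asks about cigarette consumption.

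**The concern.** A change score needs a reference value and a follow-up value, measured comparably in both arms. The plan's single named source falls short in three ways.

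- **Baseline.** The tracker does not exist for a participant until after randomisation, so it cannot supply a pre-randomisation value. Analysts could choose different baselines and windows, obtain different results, and all claim to follow the plan.
- **Comparator.** If QuitGuide does not record counts, the planned between-arm test has no comparator data from the named source.
- **Dependence on engagement.** Entries exist only on days when the participant uses the app. The two apps differ, and app engagement is itself a primary outcome. If logging is related to smoking and differs by arm, the logged means can differ when true smoking does not.

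At stake is the first-listed secondary outcome of a trial that includes preliminary efficacy among its goals. The primary feasibility and acceptability outcomes are not affected.

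**Working it through.** The documents give no SD, effect size, power or logging rate for CPD, so there is no stated figure to reproduce. The main check is a comparison of sections. The arithmetic after it is illustrative and rests on assumed inputs.

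**1. Source.** Sections 2.2 and 8.2 both name the in-app tracker alone for CPD. In the same lists, quit attempts are assigned to the TLFB, and NRT adherence has the app plus an interviewer-administered source (questionnaires in 2.2, TLFB in 8.2).

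**2. Baseline.** By the order of events in 6.3, the tracker has no pre-randomisation entries. Baseline smoking is recorded elsewhere: 30-day self-report (3.1), the CPD report used for patch assignment (5.1), tobacco history (6.2) and TLFB (6.3). None is tied to the change score. Pairing one of these with app entries at follow-up would mix two instruments within one difference.

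**3. QuitGuide.** Sections 2.2 and 8.2 assert a tracker in each app, and 4.0 and 6.4 are consistent with that. The QuitGuide description in 5.1 lists mood, craving and smoke-free or slip-day tracking, with no count. This is an assertion set against an omission, and the documents do not resolve it. If there are no counts, 0 of 30 QuitGuide participants have the measure.

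**4. Illustration of unequal logging.** Assume no true difference between arms, half of days with 0 cigarettes and half with 10 (true mean 5.0), and both arms observed only on logged days. Let p and q be the logging probabilities on smoke-free and smoking days.

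Logged mean = 10 × 0.5q / (0.5p + 0.5q)

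| p, q | Logged mean CPD |
|---|---|
| 0.9, 0.7 | 10 × 0.35 / 0.80 = 4.375 |
| 0.8, 0.5 | 10 × 0.25 / 0.65 = 3.846 |
| 0.7, 0.3 | 10 × 0.15 / 0.50 = 3.000 |

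False between-arm differences:

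- 0.8/0.5 in both arms: 0
- 0.9/0.7 against 0.8/0.5: 4.375 − 3.846 = 0.53
- 0.8/0.5 against 0.7/0.3: 3.846 − 3.000 = 0.85

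The difference is also 0 if logging is unrelated to smoking (p = q in each arm). Its sign depends on which arm logs less evenly.

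**5. Scale.** The 95% CI half-width is t(0.975, n1 + n2 − 2) × SD × √(1/n1 + 1/n2). The SDs of change are assumed. The first column uses 30 per arm (2.1, section 8.1). The second applies the 93% and 70% retention figures of 8.1 to Week 12. That is an assumption, because they are 6-month figures from prior studies: 0.93 × 30 = 27.9, about 28, and 0.70 × 30 = 21.

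| Assumed SD | 30 and 30 | 28 and 21 |
|---|---|---|
| 4 | 2.07 | 2.32 |
| 6 | 3.10 | 3.48 |
| 8 | 4.13 | 4.65 |

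The illustrative biases of 0.53 and 0.85 CPD are smaller than every half-width in the table.

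**The case against.** The strongest reply is that this is a gap in wording, with the data already planned. Section 5.2 has the TLFB asking about cigarette consumption, 6.3 and 6.4 schedule it before randomisation and at every follow-up, and 5.1 records CPD at baseline. That is correct, and it is why the remedy is cheap. It does not settle the matter, because 2.2 and 8.2 name a different source, and leaving the choice until the data are seen is what pre-specification should prevent.

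On QuitGuide, the description in 5.1 is a short summary and may not be exhaustive. It also omits NRT tracking, although 2.2 and 8.2 rely on an app tracking feature for NRT adherence. This stands: the case without QuitGuide counts is a possibility, not a finding. The parallel omission leaves the conflict open.

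App entries made between baseline and the quit date, which may be up to 4 weeks later (6.3), might be offered as a reference value. They are post-randomisation and could already be affected by the assigned app.

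The logging rates, smoking pattern and SDs above are invented, and the illustration models a mean level and not a change. This also stands, and the conclusion does not rest on it.

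Moving to the TLFB brings its own risk. At 28 and 21 completers, about 7% and 30% would lack a Week 12 value, so attrition bias is possible and not only a wider interval. Finally, 8.1 says that the study's relevance does not lie in estimating population parameters. That limits the seriousness of the point, but the plan still specifies a between-arm test, and the test needs a computable outcome.

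**Conclusion.** The concern holds and should be fixed. The firmest part is the baseline: by the protocol's own sequence, the only named source cannot supply a pre-randomisation value, and no other measure is linked to the change score. This does not depend on what QuitGuide records. The QuitGuide point is an unresolved inconsistency between 2.2 and 8.2 on one side and 5.1 on the other. At worst it leaves 0 of 30 comparator participants with the measure.

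If both apps record counts, the bias from unequal logging is unknown. The figures of 0 to 0.85 CPD rest wholly on assumed logging rates and are below the assumed-SD half-widths of 2.1 to 4.1 CPD with 30 per arm. The effect is confined to one secondary, preliminary-efficacy outcome.

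**What to change.** - In 2.2 and 8.2, define change in CPD for the between-arm comparison from the TLFB in both arms: mean CPD over one pre-specified window before the baseline visit (for example 7 days, since 5.2 leaves the TLFB timeframe open) against the same window before the Week 12 visit.
- State the rule for a missing Week 12 TLFB. One option is a main analysis of those with the interview and a sensitivity analysis that sets change to 0 for the others, with the numbers missing reported by arm. The zero-change analysis covers only one pattern of attrition and should be described as such.
- In 5.1 and 6.4, state whether each app records daily cigarette counts, so that these sections agree with 2.2 and 8.2.
- Report app-tracked CPD descriptively, by arm where available, with the number of days logged.

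The cost is a text change to the source of one secondary outcome. No visit or instrument is added. Interview recall replaces daily entry in the comparison, and the outcome comes to depend on Week 12 completion. Under the assumed 28 and 21 completers and an SD of 6, the half-width rises from 3.1 to 3.5 CPD, and differential loss would need to be considered when interpreting the result.

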## 3.0. Participants

### 3.1. Inclusion Criteria

The inclusion criteria are meant to be broad enough to capture a wide swatch of smokers with HIV. However, there are medical requirements as we will be giving participants a study drug (NRT). Also, participants will have to want to quit smoking. Therefore, the inclusion criteria are as follows:

- (1) HIV-positive
- (2) Currently engaged with an HIV care provider
- (3) Self-report smoking 5 cigarettes or more per day during the past 30 days
- (4) Age 18 years or older
- (5) Current interest in quitting smoking
- (6) Currently own a functioning Apple or Android smartphone

### 3.2. Exclusion Criteria

- (1) General Exclusion Criteria
  - a. No desire to quit smoking
  - b. Inability to provide informed consent
  - c. Any medical condition or concomitant medication that could compromise subject safety or treatment, as determined by the Principal Investigators and/or Study Physician
- (2) Medication Exclusion Criteria
  - a. Presence of contraindications for nicotine patch
  - b. Previous allergic reaction or hypersensitivity to nicotine patch (lifetime)
  - c. Current use of nicotine replacement therapy or other smoking cessation treatment (e.g., bupropion, varenicline)
- (3) Medical Exclusion Criteria
  - a. Uncontrolled high blood pressure/hypertension
  - b. Pregnant, planning to become pregnant, nursing, or becoming pregnant during the study
- (4) Alcohol/Drug Exclusion Criteria
  - a. Current untreated and unstable diagnosis of alcohol/substance abuse or dependence (eligible if past abuse/dependence and if receiving treatment and stable for >30 days)

### 3.3. Target Population Distribution

**Inclusion of Women and Minorities:** The study will be open to males and females, and all ethnic groups. The population of Durham County, North Carolina is approximately 52% female and 48% male. According to U.S. census 2013 data, the racial/ethnic composition of Durham County, NC is 53.1% Caucasian, 38.5% African-American, and 4.8% Asian, with 13.5% reporting Hispanic ethnicity. We plan to recruit a sample that is representative of the Durham County area with respect to gender and race/ethnicity.

## 4.0. Study Overview

- 1. Eligibility and Consent:** PLWH who provisionally qualify based on a phone screen will be invited to attend a remote Zoom screening visit. Informed consent will be obtained, and participants' interest in quitting, HIV and smoking statuses will be evaluated. Individuals will be screened to ensure that they own an Apple or Android smartphone, are not pregnant (if female), and are medically eligible to use NRT. Our study physician will evaluate their medical eligibility. In addition, we will obtain a signed Release of Information from potential participants to closely work with their own medical providers to monitor adverse events, dispensing of NRT, and overall participant safety.
- 2. Randomization:** Participants will be allocated to conditions using 1:1 randomization.
- 3. Interventions:** Participants will be assigned to LTQ-H or NCI QuitGuide. All participants will receive a standard 8-week course of NRT (transdermal nicotine patches starting at 21mg/24h) following recommendations contained in the U.S. Clinical Practice Guidelines.
- 4. Background Analytics:** Research staff will instruct participants on how to install the study app onto their personal smartphones and will tell them how to add a study ID in the app that will be used to retrieve background analytics information (Google Analytics) from both the LTQ-H and NCI QuitGuide apps.
- 5. Follow-Up Visits:** Visits will occur at 4, 8 and 12 weeks post-randomization. During these visits we will assess smoking and smoking abstinence, new or changes in existing adverse events and user experience with the assigned app. We will biochemically verify self-reported smoking abstinence at week 12.

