#### Nicotine Replacement Therapy (NRT) Patches

All participants will receive an 8-week course of NRT patches regardless of app assignment. Based on the number of cigarettes-per-day (CPD) reported, they will receive either a standard or adjusted course for the first 4 weeks of patch use.

	Standard	Adjusted
CPD at baseline	≥ 10	< 10
Starting dose	21 mg/24 hours	14 mg/24 hours

Following the first 4 weeks of use, participants will use 14 mg/24 hour patches for 2 weeks, followed by 7 mg/24 hour patches for the last 2 weeks (regardless of starting dosage).

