### 6.3. Baseline Visit

Participants will attend a Zoom baseline session following their eligibility determination to be randomized to the intervention. A few measures will be completed prior to randomizing the participant:

- (1) Health Changes questionnaire (adverse event and con med forms filled out if applicable)
- (2) COVID-19 & Quitting smoking Questionnaire (Adapted)
- (3) Assessing psychiatric functioning
  - a. Depression Anxiety Stress Scale-21 (DASS-21)
  - b. C-SSRS
  - c. Brief Symptom Inventory (BSI)
- (4) Fagerström Test for Nicotine Dependence (FTND)
- (5) Timeline Follow-Back (TLFB) Questionnaire
- (6) Drug Use Questionnaire (1 Month)
- (7) Internet/Smartphone Access and Use survey

After completing these measures, the participant will be randomized. They will receive either the LTQ-H app, or a standard-of-care app called QuitGuide developed by the National Cancer Institute (NCI). The RA will instruct

the participant on how to download their assigned app from the App Store/Google Play Store. The RA will give a brief overview of the assigned app to discuss the main functions and troubleshoot any major issues that may arise. They will also instruct the participant to enter their unique tracking code (similar to their subject ID) to allow us to track their background analytics data.

Following the baseline visit, we will mail 8 weeks of NRT patches to participants. We will tell participants to call/email the study team to confirm that they received their NRT. We will then instruct participants to start using the patches on the day of their quit date, which will be within 4 weeks of the baseline visit. Participants will be oriented on the best practices of using NRT based on the package instructions. There will be a brief compliance review session following the instructions in order to ensure that patients understand how to use the medication.

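### Sections 4.0 and 5.1 state different starting patch doses for eligible participants smoking 5 to 9 cigarettes per day, and nothing says which governs

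*Combined protocol and SAP*

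**What the plan says.** Section 4.0, item 3, describes the patch treatment in one sentence: "All participants will receive a standard 8-week course of NRT (transdermal nicotine patches starting at 21mg/24h". No level of smoking is attached to it.

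The nicotine patch part of Section 5.1 also covers everyone ("All participants will receive an 8-week course of NRT patches regardless of app assignment") but sets the start by reported cigarettes per day: "they will receive either a standard or adjusted course for the first 4 weeks of patch use". Its table gives a standard course, 21 mg/24 h, at 10 or more CPD at baseline, and an adjusted course, 14 mg/24 h, below 10. After the first 4 weeks both courses step down in the same way: 14 mg/24 h for 2 weeks, then "7 mg/24 hour patches for the last 2 weeks (regardless of starting dosage".

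Section 3.1, criterion 3, sets the lower limit on smoking for entry: "Self-report smoking 5 cigarettes or more per day during the past 30 days".

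Section 6.3 describes supply: "Following the baseline visit, we will mail 8 weeks of NRT patches to participants". It gives no patch strength and no CPD rule.

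**The concern.** The entry criterion and the dose table overlap. Someone smoking 5 to 9 cigarettes per day is eligible, falls in the lower column of the Section 5.1 table, and is also covered by the unqualified statement in Section 4.0. The two sections give that person different starting doses.

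The choice of words sharpens the conflict. Section 4.0 gives every participant a standard course, and Section 5.1 uses that label only for those at 10 or more CPD.

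The study is remote and the whole 8-week supply is mailed after the baseline visit. The reading applied at that step therefore decides which strengths the participant holds. The first scheduled follow-up is at Week 4. Patches start on the quit date, which falls within 4 weeks of baseline, so a participant with an early quit date could use most of the disputed 4 weeks of patches before that visit.

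**Working it through.** The check is mainly a comparison of text. No sample-size or power figure enters it.

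**Who is affected.** Eligible: CPD ≥ 5 (Section 3.1). Adjusted column: CPD < 10 (Section 5.1). The overlap is 5 ≤ CPD < 10, which is not empty.

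| Baseline CPD | Section 4.0 start | Section 5.1 start | Agree? |
|---|---|---|---|
| 10 or more | 21 mg/24 h | 21 mg/24 h | Yes |
| 5 to 9 | 21 mg/24 h | 14 mg/24 h | No |

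**Does another section settle it?**

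- Section 6.3 mails the supply without naming a strength. It adds "Participants will be oriented on the best practices of using NRT based on the package instructions", which concerns how patches are used and does not say which strength is sent.
- Section 6.2 has the study doctor judge medical compatibility with NRT. It does not have the doctor assign a dose.
- Section 7.1 makes the study doctor available to monitor and evaluate NRT use. It names no starting dose.
- Sections 4.0 and 5.1 do not refer to each other, and no order of precedence is stated.

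**Size per affected participant.** Assumptions: one patch per day, full use, and the Section 5.1 step-down applied after either start. Section 4.0 gives no step-down of its own, but Section 5.1 says its step-down holds "regardless of starting dosage". The first phase is 4 × 7 = 28 days and each later phase is 2 × 7 = 14 days.

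| | 21 mg start | 14 mg start | Difference |
|---|---|---|---|
| First 4 weeks | 28 × 21 = 588 mg | 28 × 14 = 392 mg | 196 mg |
| Next 2 weeks | 14 × 14 = 196 mg | 14 × 14 = 196 mg | 0 |
| Last 2 weeks | 14 × 7 = 98 mg | 14 × 7 = 98 mg | 0 |
| Total labelled dose | 882 mg | 686 mg | 196 mg |
| Patches | 28 + 14 + 14 = 56 | 42 + 14 = 56 | 0 |

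The ratio of starting doses is 21/14 = 1.5. The number of patches is the same, so a patch count would not show which reading had been used.

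**Reach into the outcomes.** Section 8.2 analyses NRT adherence as use of an optimal amount (yes/no) and as the percentage used as directed. If these are counted in patches or days, the denominator is 56 under both readings and nothing changes. If they are judged by strength or mg, this subgroup has no single reference regimen.

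**The case against.** The strongest reply is that Section 4.0 is only an overview. It has one parenthetical remark on patches, with no step-down, phase lengths or CPD rule, so nobody could dispense a full course from it. Section 5.1 is the dedicated section and the only complete regimen, and its wording on the step-down shows that more than one starting dose was intended there. Staff would also have the smoking data before mailing: tobacco history is taken at screening, and the Fagerström test and Timeline Follow-Back at baseline. A study doctor reviews each case. On this view the finding is an outdated summary sentence with no shown effect on any primary outcome, on power or on the comparison of the apps.

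Much of this stands. It is reasonable to infer that Section 4.0 was not updated, and nothing shows that staff would dispense from it. The mg totals join the Section 4.0 start to the Section 5.1 step-down. What the documents state directly is only 21 against 14 mg/24 h. Section 4.0 also cites the U.S. Clinical Practice Guidelines, which cannot be consulted here, so whether that reference was meant to carry a dose adjustment cannot be judged.

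The reply does not remove the contradiction. Section 4.0 covers all participants without qualification, the documents do not say that it yields to Section 5.1, and having the smoking data does not tell staff which rule to apply to them.

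**Conclusion.** The concern holds. For eligible participants smoking 5 to 9 cigarettes per day, the protocol states two starting doses, 21 and 14 mg/24 h, for the first 4 weeks of patch use. At 10 or more per day the sections agree. Under the assumptions above, the gap is at most 196 mg of labelled dose per affected participant. The number affected is not given and cannot be derived.

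The limits are clear. Both arms follow the same NRT rule, so the conflict does not in itself bias LTQ-H against QuitGuide. No sample-size or power figure depends on it, and no effect on a primary outcome was identified. Adherence is touched only if it is measured by strength or mg. The point is a must-fix on one ground: the protocol contradicts itself on study-drug dose for people its own criteria admit. This review takes no position on which dose is right.

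**What to change.** Reconcile Section 4.0, item 3, with Section 5.1 so that both carry the same regimen statement. Add a cross-reference to that statement at the mailing step in Section 6.3, so that the strengths sent follow from one rule. Check the dispensing and consent materials against it. The consent pages were not available here, so no discrepancy in them is alleged. The choice of regimen belongs to the investigators and study physician.

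The cost is a one-sentence correction, one cross-reference and a document check. Sample size, visits and analyses do not change.
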